5. ANALYSIS METHODS

5.1. General Principles

5.1.1. General Methodology

In general, all efficacy, safety and PK variables will be summarized using descriptive statistics and graphs as appropriate. Continuous variables will be summarized by descriptive statistics (observed number (n), mean, standard deviation, minimum, 25% percentile (Q1), median, 75% percentile (Q3), and maximum). Categorical variables will be summarized in frequency tables (frequencies and percentages).

Time to event variable will be analyzed using Kaplan-Meier method and summarized with median, 25% and 75% percentiles with their corresponding 95% confidence intervals (CI) which are calculated from a log-log transformation based on the method by [Brookmeyer and Crowley \(1982\)](#). Individual data will be presented in patient listings.

Analyses will be implemented using SAS Enterprise® Version 8.3 or higher (SAS Institute, Cary, North Carolina, USA). The International Conference on Harmonization (ICH) numbering convention, i.e. ICH-E3, will be used for all tables and listings.

Unless otherwise specified, analyses will be summarized:

- Efficacy analysis: by dose level for escalation stage (part 1) and by disease type for dose expansion (part 2).
- Analysis besides efficacy: by dose level and total for escalation stage (part 1) and by disease type and total for dose expansion (part 2).

In addition, main efficacy analysis will be repeated by IDH naïve/treated status (as defined in [Section 5.2.4](#)) and dose level for escalation stage (part 1) and by disease type for dose expansion (part 2).

Analysis will be conducted on the basis of first dose of study drug that a patient received. Hence, all summary tables, listings, and figures (TLFs) will be presented by treatment groups as defined in [Table 13](#).

Table 13 Group Display in TLFs

Part of the study	Treatment Group	Treatment Description in Data Display
Part 1 - Dose Escalation	1	Cohort 1- XX mg
	2	Cohort 2- XX mg
	3	Cohort 3- XX mg
	4	Cohort 4- XX mg
	5	Cohort 5- XX mg
	6	Cohort 6- XX mg
	7	Cohort 7- XX mg
	8	Cohort 8- XX mg
Part 2 - Dose Expansion at HMPL-306 XX mg*	1	Cohort A: AML

*As only one patient at HMPL-306 [REDACTED] mg was enrolled in Part 2 Dose expansion Cohort A, this patient will be combined into Part 1 Dose escalation Cohort 8 [REDACTED] mg in all the summary tables and figures.

For continuous data, unless otherwise specified, the mean, median, Q1, and Q3 will be presented with 1 more significant digit than the original values, and standard deviation and standard error (SE) will be reported with 2 more significant digits than the original values. The minimum and maximum should report the same significant digits as the original values. The derived variables will be presented with 1 decimal place. Percentages will be reported with 1 decimal point; if the count is 0, no percentage will be presented. Value of percentage less than 1% will be presented as “<1%.” Value of percentage less than 100% but \geq 99.5% will be presented as “>99%.” Any rounding will be done after all calculations are made.

5.1.2. Handling Missing Data

In general, the observed case (OC) data for a visit will consist of the actual observations recorded for the visit. If missing, the OC data will remain missing — no missing imputation will be performed. Safety analyses will be conducted on the OC data only.

However, imputation of missing AE and concomitant medication onset and stop dates will be used to determine the status of each AE and the prior/concomitant status of each medication. Other imputations are applied for calculations, if needed. However, the imputed dates should not be shown in listings.

For demographic and baseline characteristics, each variable will be analyzed and/or summarized using the available data. Unless otherwise specified, patients with missing data will be excluded only from analyses for which data are not available.

5.1.2.1. Adverse Events Start/End Date

AEs with onset/end dates that are partially/completely missing will be imputed as follows.

(i) AE start date:

- If the AE onset date is completely missing, the AE start date will be imputed as the reference start date;
- If the AE onset date is partial missing, then
 - If both the year and the month are available and the year and the month are the corresponding year and month of the reference start date, then the AE start date will be imputed as the reference start date;
 - If both the year and the month are available and the year and the month are not equal to the corresponding year and month of the reference start date, then the AE start date will be imputed as the 1st day of the month;
 - If only the year is available and the available year is the corresponding year of the reference start date, then the AE start date will be imputed as the reference start date;
 - If only the year is available, and the available year is not equal to the corresponding year of the reference start date, then the AE start date will be imputed as the January 1st of the year

(ii) AE end date will be imputed as below for the partial date only, the imputation rules only apply when the AE is not ongoing:

- If both the year and the month are available, AE end date will be imputed as the last day of the month;
- If only the year is available, AE end date will be imputed as the December 31st of the year.

If the imputed AE end date is after the death date for patients known to be dead at end of study or cut off date, the date of the death will be used for AE end date. If the imputed AE end date is after the last known alive date for patients alive at the end of study or cut off date, the date of last known alive date will be used for AE end date.

For AE continuing at the cut-off date, the end date will not be imputed and instead will be reported as “ongoing”.

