4. ENDPOINTS

4.1. General Principles for Derived and Transformed Data

4.1.1. Reference Start Date and End Date and Study Day

(1) Reference start date

Dose escalation part:

For efficacy analysis, reference start date (Day 1) is defined as the first date when a non-zero dose of study treatment in continuous dosing cycle (i.e. excluding single oral dose from the PK week) is administrated.

For safety analysis, reference start date (Day 1) is defined as the first date when a non-zero dose of study treatment (i.e. including single oral dose from the PK week) is administrated.

Dose expansion part:

Reference start date (Day 1) is defined as the first date when a non-zero dose of study treatment is administrated.

(2) Reference end date

Reference end date is defined as the last date when a non-zero dose of study treatment is administered.

(3) Study day

Study day will be calculated from the reference start date, and it will be used to show start/stop day of assessments or events relative to the start date of study treatment.

- If the date of the event is on or after the reference start date, study day = (date of event – reference start date) + 1.
- If the date of the event is prior to the reference start date, study day = (date of event – reference start date).

Note that, the day of the first dose of study drug is day 1 and the day before it is day – 1, not day 0.

In the situation where the event date is partial or missing, the date will appear partial or missing in the listings.

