4.4.2. Adverse Events (AEs)

All AEs will be coded from verbatim text to preferred term (PTs) and grouped by system organ class (SOC) using the Medical Dictionary for Regulatory Activities (MedDRA) version 27.1 or higher. AEs will be collected from the time of signature of informed consent throughout the treatment period. AEs will be graded by investigator according to National Cancer Institute (NCI) Common Terminology Criteria for Adverse Events (CTCAE) v5.0. Missing severity grade will not be imputed, and will be summarized as 'Missing Grade' category in the by-grade analysis.

An AE is considered a TEAE:

(i) If one of the criteria is met:

- 1) If the onset date is on or after the start of study treatment until 30 days after the last dose or prior to the start of a subsequent anti-tumor therapy (whichever comes first), or if the onset date is missing; or
- 2) If the AE has an onset date before the start of study treatment, but worsened in severity after the study drug administration (i.e. SAE start date is on or after the start of study

treatment until 30 days after the last dose or prior to the start of a subsequent anti-tumor therapy (whichever comes first);

(ii) Beyond 30 days after the last dose or after the start of a subsequent anti-tumor therapy (whichever comes first), treatment-related SAEs will also be considered as TEAEs.

Investigator assessed AEs causality to study drug will be classified as "Related" and "Not Related". An AE with a missing causality will be classified as "Related" to study drug.

Other AE variables include treatment-related AEs, AEs of special interest (AESI), COVID-19 related AEs, AEs leading to study drug modifications (i.e. dose interruption, dose reduction, or study drug withdrawal), AEs leading to death, and SAEs. The AESI information will be identified programmatically by SMQ/PT.

For AEs which are not on-going, duration of AE (days) is defined as AE end date – AE start date +1; for on-going AEs, the end date will be listed as 'Ongoing'.

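### AE start dates imputed as first dose are not checked against the AE end date, so some AEs that ended before dosing are classed as treatment-emergent

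*SAP*

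**What the plan says.** SAP 5.1.2.1 has five rules for an incomplete AE onset date. Three of them lead to the reference start date:

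- No onset date at all: "If the AE onset date is completely missing, the AE start date will be imputed as the reference start date".
- Day unknown, where "the year and the month are the corresponding year and month of the reference start date, then the AE start date will be imputed"; the value used is again first dose.
- Year only: "If only the year is available and the available year is the corresponding year of the reference start date", with the same result.

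The other two cover a known month or year that differs from first dose. For the month, "then the AE start date will be imputed as the 1st day of the month"; for the year, 1 January is used.

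For safety analyses in Part 1, "reference start date (Day 1) is defined as the first date when a non-zero dose of study treatment (i.e. including single oral dose" of the PK week) is given, so the comparison date is the PK-week dose (SAP 4.1.1).

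On end dates, SAP 5.1.2.1 says "AE end date will be imputed as below for the partial date only", taking the last day of the month or year. The only cross-checks cap an imputed end date at death or at the last known alive date.

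SAP 5.1.2 says that "imputation of missing AE and concomitant medication onset and stop dates will be used to determine the status of each AE". SAP 4.4.2 collects AEs from informed consent and counts an AE as a TEAE if its onset is on or after the start of treatment, "or if the onset date is missing". It defines duration as end minus start plus one day.

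Protocol 9.2.4 limits TEAEs to AEs that started or got worse on or after first dose.

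**The concern.** Because collection starts at consent and screening can run from Day −28 to Day −1, AEs that resolve before dosing belong in the database. If such an AE has an incomplete onset date that falls under one of the three rules, its start is moved to first dose even though the recorded end is earlier. It is then a TEAE by rule, although it neither started nor worsened on treatment.

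Safety is the primary endpoint, and non-efficacy tables are shown by dose level in cohorts of at least 3 patients. One patient wrongly counted under a preferred term, with no other TEAE of that term, adds 1/3 = 33 percentage points in a cohort of 3, or 1/6 = 17 in a cohort of 6.

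Duration may also be affected. Under the SAP formula the smallest possible value is 1 day, so zero or a negative value is impossible for a real event.

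**Working it through.** The plan states no figure on this point, so there is none to reproduce. The check applies the rules as written to hypothetical records.

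**Inputs.** Start-date rules from SAP 5.1.2.1; TEAE rule and duration formula from SAP 4.4.2; use of imputed dates from SAP 5.1.2. Assumed for illustration: first dose 20 March 2024.

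**Formulas.** Date test for a TEAE: imputed start ≥ first dose. Duration = end − imputed start + 1. The duration column assumes that imputed starts feed the formula.

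| Recorded onset | Recorded end | Imputed start | TEAE by date | Duration (days) |
|---|---|---|---|---|
| March 2024, day unknown | 10 Mar 2024 | 20 Mar 2024 | yes | 10 − 20 + 1 = −9 |
| 2024, month and day unknown | 10 Mar 2024 | 20 Mar 2024 | yes | −9 |
| completely missing | 10 Mar 2024 | 20 Mar 2024 | yes | −9 |
| March 2024, day unknown | 19 Mar 2024 | 20 Mar 2024 | yes | 19 − 20 + 1 = 0 |
| February 2024, day unknown | 10 Mar 2024 | 1 Feb 2024 | no | 39 |
| 2023, month and day unknown | 10 Mar 2024 | 1 Jan 2023 | no | 435 |
| March 2024, day unknown | 25 Mar 2024 | 20 Mar 2024 | yes | 25 − 20 + 1 = 6 |

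The first four rows are wrong: the end date proves that the event was over before dosing. The February and 2023 rows are correctly left as pre-treatment. In the last row the onset could fall either side of first dose, and the SAP reasonably keeps the event as a TEAE.

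**Range of duration.** An AE that ended on Day −k is given 1 − k days. For k = 1 to 28 this runs from 0 to −27: negative for 27 of the 28 end days, and zero when the AE ended the day before dosing.

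**Effect of an end-date check.** Take the simplest form: start = the earlier of the imputed start and the end date. The first three rows then start on 10 March, fall before dosing, and last 1 day. The fourth starts on 19 March and also lasts 1 day. The last three rows do not change. For March onset with the day unknown, the earliest start that fits the record is 1 March if consent was given by then, so 10 − 1 + 1 = 10 days; the TEAE status is the same.

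**One check is not enough.** For a completely missing onset, the separate missing-onset clause in SAP 4.4.2 still makes the event a TEAE whatever start date is imputed. Both sections need the condition.

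**Search for a safeguard.** Neither document has a rule that removes an AE whose end precedes first dose, and SAP Section 7 lists no change to the TEAE definition. Elsewhere the SAP does make such checks: imputed death date against last known alive date (5.1.2.4), last dose against death, end of treatment and end of study (5.1.2.5), diagnosis against first dose (5.1.2.6), and subsequent therapy against the reference end date (5.1.2.7).

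**The case against.** The strongest defence is that assigning an unclear onset to first dose is a deliberate conservative choice, in line with counting missing causality as related in SAP 4.4.2. That stands wherever the timing is truly unknown. It does not cover an event whose end date shows that it was over before dosing.

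A second defence is rarity. The AE must begin after consent, resolve before first dose, have an onset that is missing or matches the dosing month or year, and have an end date known to precede dosing. A partial end date in the dosing month is imputed to the end of that month, so no conflict arises there. The schedule footnotes may also narrow pre-dose collection to AEs caused by protocol procedures, although Protocol 8.2.1 collects all AEs regardless of attribution. All this makes a small number likely, but does not make it zero.

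Third, SAP 5.1.2 ties AE date imputation to AE status and mentions other calculations only in general terms, so use of imputed starts in the duration formula is an inference. Duration is summarised only for AESIs, namely hepatic events and differentiation syndrome. The latter is a treatment effect, so a pre-dose case is implausible. Imputed dates are not shown in listings. This stands, and it leaves resolved pre-dose hepatic AESIs as the realistic case for duration.

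A reader might infer that every partial or missing AE start date is moved to first dose, or that negative durations are certain to be reported. The documents support neither: two of the five rules use the 1st of the month or 1 January, and the duration effect is conditional.

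**Conclusion.** The point holds as a narrow gap in the specification. Under three of the five rules in SAP 5.1.2.1, and under the missing-onset clause in SAP 4.4.2, an AE with a recorded end before first dose is classed as treatment-emergent, against the protocol's own definition. This follows from the text without further assumption, because SAP 5.1.2 uses imputed dates to settle AE status.

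The zero or negative duration, from −27 to 0 days for ends between Day −28 and Day −1, assumes that imputed starts enter the duration formula. Its effect on summaries is limited to AESIs.

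The documents do not say how many AEs have incomplete onset dates, so the effect on TEAE counts cannot be estimated. It is probably small, and a reader should not infer that the safety tables are materially inflated. The point is minor; it is worth correcting because safety is the primary endpoint, the cohorts are small and the remedy is cheap.

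**What to change.** Change two places in the SAP.

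- **5.1.2.1.** Add an end-date condition. It applies if the AE end date is before the reference start date, using the complete date or, if partial, its latest possible value. The imputed start must then not be later than the end date, and the AE is not a TEAE. For the start, use the earliest date that fits the known parts and is not before consent. If the onset is completely missing, use the end date itself.
- **4.4.2.** Restrict the missing-onset clause, so that a missing onset counts as a TEAE only when the end date is not known to be before the start of study treatment.

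The cost is a few lines of text and a small programming change, with no new data. AEs that are ongoing, have no end date, or have a partial end date that could fall on or after first dose remain TEAEs, so the conservative handling of uncertain timing is kept.

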5.1.2.2. Concomitant Medication/Procedure/Surgery Start/End Date

Concomitant Medication/Procedure/Surgery with onset/end dates that are partially/completely missing will be imputed as follows.

(i) start date:

- 1st day of the month will be used to impute the start date if only the day is missing
- January 1st will be used to impute the start date if both the day and month are missing
- If the date is completely missing, then the day before the reference start date will be imputed as the start date.

(ii) end date:

- Last day of the month will be used to impute the end date if only the day is missing
- December 31st of the year will be used to impute the end date if both the day and month are missing
- If the date is completely missing, assign ‘continuing’ status to the end date

If the imputed end date is after the death date or last known alive date, the date of the death or last known alive date will be imputed as the Concomitant medication/procedure/surgery end date.

5.1.2.3. Last Known Alive Date

When a partial last known alive date is reported, below rules will be used:

- If only the day of the month is missing, then last known alive date will be imputed as 1st of the month;
- If both the day and the month are missing, then last known alive date will be imputed as 1st January of the year.

5.1.2.4. Date of Death

When a partial death date is reported, below rules will be used:

- If only the day of the month is missing, then date of death will be imputed as 1st of the month.
If the imputed date of death is earlier than last known alive date, then date of death will be replaced by last known alive date + 1 day.

If year is missing or both year and month are missing, then no imputation will be applied.

5.1.2.5. The Last Dose Date of Study Drug

When a partial last dose date of study drug is reported, below rules will be used:

- If only the day of the month is missing, then it will be imputed as the last day of the month;
- If both the day and the month are missing, then it will be imputed as the December 31st of the year.

If the imputed last dose date of study drug is later than date of death (if the subject died) / last known alive date (if the subject is not known to die) / EOT date / EOS date, then it will be replaced by the earliest of the above.

If the last dose date of study drug is complete missing, then it will be imputed by the earliest of the above.

5.1.2.6. Initial Diagnosis Date

When a partial initial diagnosis date is reported, below rules will be used:

- If the date is completely missing, do not impute;
- If both the day and the month are missing, then it will be imputed as July 1st of the year;
- If only the day of the month is missing, then it will be imputed as 15th of the month.

If the imputed initial diagnosis date is later than the first dose date of study drug, it will be replaced by the first dose date of study drug.

5.1.2.7. Subsequent Anti-cancer Therapy Date

When a partial subsequent anti-tumor therapy start date is reported, every effort will be made to identify the precedence relationship of starting date of subsequent anti-tumor therapy relative to the reference end date. Below rules will be used:

- If the date is completely missing, subsequent anti-tumor therapy date will be imputed as reference end date + 1;
- If only the day is missing, 15th day will be imputed as the subsequent anti-tumor therapy date;
- If both the day and the month are missing, then July 1st will be imputed as the subsequent anti-tumor therapy;

If the imputed date is earlier than reference end date, then it will be replaced with reference end date + 1, if the imputed date is later than the date of death or last known alive date, it will be replaced with the date of death or last known alive date.

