6.1.18 End of Treatment Visit

Patients who have completed the study or have discontinued study treatment will be asked to return to the investigational site to have safety examinations and assessments within 7 days (± 3 days) after the last dose of the study drug.

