4.1.4. Treatment Period

Unless otherwise specified, the treatment period is defined as the duration from the date of the first study drug administration to 30+7 days (7-day window only replies to parameters collected by visit) after the date of last administration of study drug or prior to the start of a subsequent anti-tumor therapy (whichever comes first). For safety data, only the assessments/events collected during the treatment period will be summarized.

The worst post baseline is defined as the worst assessments/events during the treatment period including both scheduled and non-scheduled visit. Only the on-treatment safety assessments will be included in the summary tables.

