5	Early discontinuation (lost to follow-up or withdrawal of consent) of study without death or relapse (or PD)	Date of last adequate tumor assessment	Censored
6	Subsequent anti-tumor therapy started prior to relapse (or PD) or death	Date of last adequate assessment prior to or on date of initiation of subsequent anti-tumor therapy	Censored
7	Death or relapse (or PD) after two or more consecutive missed or inadequate tumor assessment visits	Date of last adequate tumor assessment prior to missed visits	Censored

PD is only applicable for the duration of objective response.

Note: An adequate tumor assessment is defined as an assessment where the Investigator determined response is CR_{MRD}-, CR, CRh, CRI, MLFS, PR, SD, and PD. If PD and subsequent anti-cancer therapy occur on the same day, will assume that the progression was documented first, e.g. outcome is progression and the date is the date of the assessment of progression.

(a) Determination of one missing or inadequate assessment

The following provides the rules for determining whether one tumor assessments is missed, of note, the relative day in the rules refers to the first dose date of study drug from Cycle 1 in continuous cycle.

- If the tumor assessment date is prior to day 1 of week 23 (relative day $< (24 - 1) \times 7 + 1 = 162$), and the difference between the tumor assessment date and the next adjacent adequate tumor assessment ≥ 63 days (8 weeks * 7 + 7), then the tumor assessment is considered as occurring after one missing tumor assessment;
- If the tumor assessment date is on or after day 1 of week 23 (relative day $< (24 - 1) \times 7 + 1 = 162$), and the difference between the tumor assessment date and the next adjacent adequate tumor assessment ≥ 98 days (12 weeks * 7 + 14), then the tumor assessment is considered as occurring after one missing tumor assessment.

(b) Determination of two or more consecutive missing or inadequate assessments

The following provides the rules for determining whether two or more consecutive tumor assessments are missed.

- If the tumor assessment date is prior to day 1 of week 15 (relative day $< (16 - 1) \times 7 + 1 = 106$), and the difference between the tumor assessment date and the next adjacent adequate tumor assessment ≥ 126 days ($= 2 * (8 \text{ weeks} * 7 + 7)$), then the tumor assessment is considered as occurring after two or more consecutive missing tumor assessments;

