4.2.7. Progression-free Survival

Progression-free Survival (PFS) is defined as the time (months) from the start of study treatment from Cycle 1 in continuous cycle (i.e. not from the date of single oral dose from the PK week for the dose escalation part) to disease progression, or relapse, or death due to any cause, whichever occurs first. More specifically, PFS will be determined using all the assessment data up until the last evaluable visit prior to or on the date of

- (i) disease progression (at least 2 cycles of study drug should be administered to determine PD) or relapse as defined by 2017 ELN criteria for AML patients, or
- (ii) withdrawal of consent; or lost to follow-up, or
- (iii) receiving subsequent anti-tumor therapy, whichever is earlier.

Patients without report of PD or death due to any cause at the time of analysis are censored as described in [Table 7](#) below.

Table 7 Outcome and Event or Censoring Dates for PFS

Rule	Situation	Date of Progression or Censoring	Outcome
------	-----------	----------------------------------	---------

1	PD/relapse documented between schedule tumor assessment visit or after one missing tumor assessment visit	Date of first documented disease progression/relapse	Event
2	Death without PD/relapse between schedule tumor assessment visit or death on or before the second scheduled visit or death after one missing tumor assessment visit	Date of death	Event
3	No baseline or post-baseline tumor assessments available and subject dose not die	Date of first administration of study treatment	Censored
4	No death or PD/relapse by the time of data cut-off for final analysis	Date of last adequate tumor assessment prior to or on analysis data cutoff date	Censored
5	Early discontinuation (lost to follow-up or withdrawal of consent) of study without death or PD/relapse	Date of last adequate tumor assessment	Censored
6	Subsequent anti-tumor therapy started prior to PD/relapse or death	Date of last adequate assessment prior to or on date of initiation of subsequent therapy visit	Censored
7	PD/relapse or death after missed or inadequate two or more consecutive tumor assessment visits	Date of last adequate tumor assessment prior to missed visits or date of first administration of study treatment (if no post-baseline tumor assessment)	Censored

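### SAP 5.1.2.7 imputes incomplete subsequent-therapy start dates without regard to documented PD/relapse, so a PD found after the last dose can be censored and the safety windows cut short

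*SAP*

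**What the plan says.** SAP 5.1.2.7 has three imputation rules for the start of subsequent therapy:

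- Date wholly missing: "If the date is completely missing, subsequent anti-tumor therapy date will be imputed as reference end date + 1".
- Day missing: "If only the day is missing, 15th day will be imputed as the subsequent anti-tumor therapy date".
- Day and month missing: "If both the day and the month are missing, then July 1st will be imputed as the subsequent anti-tumor therapy".

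An imputed date before the reference end date is moved to the day after it. A date beyond death or last known alive date is pulled back to that date. SAP 4.1.1 defines the reference end date as the last non-zero dose. PD and relapse are not mentioned.

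The imputed date is then used in two places.

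- **Efficacy.** PFS Rule 6 (SAP Table 7) censors in the situation "Subsequent anti-tumor therapy started prior to PD/relapse or death", at the last adequate assessment up to the therapy date. Duration of response has the matching rule (SAP Table 2): "Subsequent anti-tumor therapy started prior to relapse (or PD) or death". EFS Rule 6 (SAP Table 4) does the same for patients with CR by 24 weeks, and the BOR evaluation period (SAP 4.2.1) also stops at new therapy. Notes under Tables 2 and 7 put progression first when both fall on the same day.
- **Safety.** The treatment period (SAP 4.1.4), the TEAE window (SAP 4.4.2) and on-treatment deaths (SAP 5.2.11.3) end at new therapy if that comes before last dose + 30 days.

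**The concern.** Rule 6 depends on the order of two dates, new therapy and PD/relapse, but the imputation secures only the order of new therapy and last dose. This matters when PD is first documented after the last dose, and the protocol plans for that. Tumor evaluation is scheduled at the end-of-treatment (EOT) visit, where patients return for "safety examinations and assessments within 7 days" (±3) of the last dose. It then continues every 12 weeks for patients who stopped for reasons other than progression (Protocol 6.1.19).

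In such a patient the imputed start can land before a PD that truly came first. The event then becomes a censoring at the preceding assessment, which the schedule places 8 weeks earlier during the first 24 weeks and 12 weeks earlier after that.

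On the safety side, an imputed date alone can close the 30-day post-dose window although the patient was still being observed. Safety is the primary endpoint of both parts.

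**Working it through.** The plan gives no figure on this point, so there is none to reproduce. The check applies the date rules to cases where therapy truly began after PD.

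**Inputs from the documents:** the SAP 5.1.2.7 rules and bounds; Rule 6 and the same-day rule; EOT at 7 ± 3 days after last dose (Protocol Appendices 1 and 2); efficacy follow-up every 12 weeks ± 14 days; the safety window of last dose + 30 days.

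**Assumptions, not in the documents:** last dose equally likely on any day of a 365-day year; PD 4–10 days after last dose (EOT) or 77–105 days after (efficacy follow-up); therapy 1–30 days after PD, each lag equally likely.

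**Worked cases**

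| Last dose | PD | True start | Recorded | Imputed | Result |
|---|---|---|---|---|---|
| 10 Mar | 18 Mar | 25 Mar | month and year | 15 Mar | true event censored |
| 10 Mar | 17 Mar | 2 Apr | nothing | 11 Mar | true event censored |
| 1 Aug | 24 Oct | 10 Nov | year | 1 Jul, raised to 2 Aug | true event censored |
| 1 Mar | 10 Mar | 5 Mar | month and year | 15 Mar | true censoring becomes an event |

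**Day missing.** With lag d in a month of L days, the order flips when PD falls on day 16 or later and PD day + d ≤ L. That is L − 15 − d days, while this is positive. Summed over d:

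- 31-day month: 15 + 14 + … + 1 = 120
- 30-day month: 14 + … + 1 = 105
- 28-day month: 12 + … + 1 = 78

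Over the year: (7 × 120 + 4 × 105 + 78) / (365 × 30) = 1,338 / 10,950 = 12.2%. The last dose + 1 floor does not help, because it also precedes a PD at day +4 or later. The share depends strongly on the lag. In a 30-day month it is 14/30 = 47% at 1 day, 12/30 = 40% at 3, 8/30 = 27% at 7, 5/30 = 17% at 10 and 1/30 = 3% at 14.

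**Day and month missing.** The order flips when PD falls from 2 July on and therapy starts in the same year: 183 − d days. Averaged over d = 1 to 30: (183 − 15.5) / 365 = 45.9%.

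**Wholly missing.** Last dose + 1 is earlier than any PD at day +2 or later: 100%.

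Enumerating every case under the coded rules gives 12.2%, 45.9% and 100% for PD at EOT, and 12.3%, 45.9% and 100% for PD at efficacy follow-up. With PD on the last-dose day all three are 0%.

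**Safety days lost**

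| PD timing | Wholly missing | Day missing |
|---|---|---|
| At EOT | mean 20.7, maximum 30 | mean 3.7, maximum 16 |
| On last-dose day | mean 14.5, maximum 29 | mean 3.4, maximum 16 |

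The maximum of 16 arises when the true start is the 31st and the imputed start the 15th. This loss does not require PD after the last dose.

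**Can one flip matter?** Take an invented cohort of three (the protocol minimum per dose level) with PFS events at 2, 4 and 6 months, median 4.

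- Flip the middle event to a censoring 8 weeks earlier, at 4 − 56/30.4375 = 2.2 months. Survival is 2/3 after month 2, then falls to 0 at month 6, so the median becomes 6.
- Flip the last event instead, to 6 − 1.84 = 4.2 or 6 − 2.76 = 3.2 months (8 or 12 weeks earlier). The median stays at 4.

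**The case against.** A reader might infer that the rule inflates PFS and duration of response throughout the study, that post-dose AEs and deaths are lost, and that any single flip moves the median. The documents do not support that reading.

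- **Many progressions are protected.** Tumor evaluations fall on treatment days (Day 1 of Cycles 3, 5, 7 and so on), PD requires discontinuation, and Protocol 7.2.2.2 allows for drug already dispensed when PD is found. Where dosing reaches or passes the PD date, the floor keeps the order right. An EOT visit on the last-dose day or the day after, which the wording within 7 days could allow, is also safe. This stands, and it limits the problem to PD documented after the last dose.
- **Direction is not fixed.** The 1/5/10 March case turns a censoring into an event. Only the wholly-missing rule errs in one direction, because it takes the earliest date the floor permits.
- **Safety data are not erased.** Treatment-related SAEs remain TEAEs beyond the window, all AEs are listed, and deaths are tabulated overall and by period. A death is reclassified, not lost. Unrelated SAEs and non-serious AEs do leave the summary tables.
- **The median need not move,** as the second illustration shows.
- **Weight.** The efficacy endpoints are secondary and descriptive, and the number of incomplete dates is not given. This also stands.
- **A blanket PD bound could itself be wrong.** Responders may leave for transplant and relapse later (Protocol 6.2.1.2). Records showing that order must override any imputation, and the fix needs to say so.

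None of this removes the gap. Where PD follows the last dose and the therapy date is incomplete, the rule can contradict an order that the known date parts leave open.

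**Conclusion.** The point holds conditionally. SAP 5.1.2.7 can place new therapy before a PD or relapse that truly preceded it, but only when that PD or relapse was documented after the last dose and the therapy date is partial or missing. Among such cases about 12% of true events become censorings with the day missing and about 46% with day and month missing. With the date wholly missing it is every PD later than last dose + 1. The first two figures rest on the assumed even spread of lags from 1 to 30 days; shorter lags raise the day-missing share and longer ones lower it.

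The shortening of the treatment-period, TEAE and on-treatment-death windows is a separate effect and needs only an incomplete therapy date.

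The overall effect on the study cannot be sized, because the count of affected dates is unknown. In cohorts this small one flip could change a Kaplan-Meier estimate, but it need not. This is a cheap improvement to make before database lock, not a flaw that undermines the analysis.

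**What to change.** Add two rules to SAP 5.1.2.7:

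> For duration of response, PFS, EFS and BOR: where the known date parts allow it, and no other record (such as transplant or follow-up data) shows that therapy began before PD/relapse, the imputed start is no earlier than the first documented PD/relapse. A wholly missing start is the later of reference end date + 1 and the PD/relapse date. Ties count as progression first.
>
> For the treatment-period, TEAE and on-treatment-death windows: use the latest start compatible with the known date parts, so that a wholly missing date does not shorten the window of last dose + 30 days.

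State the tie convention for EFS as well, since the existing notes stand only under Tables 2 and 7. With the PD bound, none of the enumerated true events is censored. The bound does not restore the safety window, so both rules are needed.

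The cost is a few sentences and two derived dates for one variable. A patient who truly switched just before PD and has an incomplete date would be counted as an event, and some AEs after the true switch may enter the summaries.
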